5.5.1 Treatment of Vaccinia Vaccination Complications

5.5.1.1 Vaccinia Immune Globulin (VIG)

Vaccinia Immune Globulin (VIG): First-line treatment of some of the complications of vaccinia caused by dissemination of vaccinia virus (severe cases of inadvertent inoculation involving extensive lesions or if comorbid conditions exist, severe cases of generalized vaccinia in patients that are systemically ill and whose condition might be toxic or who have serious underlying immunosuppressive illnesses, eczema vaccinatum, and progressive vaccinia) is with VIG. VIG is contraindicated, however, for the treatment of isolated vaccinia keratitis. VIG is a sterile solution of the immunoglobulin fraction of pooled plasma from individuals inoculated with vaccinia vaccine. VIG is only available through the CDC's Strategic National Pharmaceutical Stockpile by contacting the CDC's Clinician Information Line at [name] or the Director's Emergency Operations Center (DEOC) at [contact]. Upon receipt of a call from a patient or upon direct observation of a patient or contact who manifests signs and symptoms of any of the above conditions, the investigator should place a call to the CDC as soon as possible: 1) to initiate review of the clinical case, 2) to seek consultation on the

appropriateness of VIG therapy, 3) to determine the appropriate VIG dose and dosing method for administration, if VIG therapy is required, and 4) to determine how to access and have the appropriate doses of VIG delivered. Early institution of VIG therapy is advised following recognition of clinical symptoms compatible with some vaccinia complications (eczema vaccinatum, severe generalized vaccinia, progressive vaccinia, and some cases of inadvertent inoculation). The effectiveness of VIG therapy appears to be time dependent. VIG has not proven to be of benefit in the treatment of post-vaccinia encephalitis, and is contraindicated for treatment of isolated vaccinia keratitis due to the increased risk of corneal scarring. A new IV formulation of VIG that has a lower level of aggregated protein allowing it to be used by either the IM or IV route is available through the CDC. This formulation will most likely be preferred for administration and the CDC will instruct investigators regarding appropriate dosing and method of administration based on the formulation and availability. There is no guarantee that VIG will successfully treat complications. At present, there are no other anti-viral therapies of proven benefit for the treatment of vaccinia-related complications.

5.5.1.2 Cidofovir (Vistide®, Gilead Sciences)

Cidofovir (Vistide®, Gilead Sciences): Cidofovir is an FDA-approved antiviral drug for the treatment of CMV retinitis among patients with AIDS. Cell-based *in vitro* studies and animal model studies have demonstrated this agent's antiviral activity against certain orthopoxviruses. Currently, its efficacy in the treatment of vaccinia-related complications in humans is unknown. According to the CDC, VIG is recommended as first line of therapy. Cidofovir may be considered as a secondary treatment, and will only be used when VIG therapy is not effective [Medical Management of Smallpox (Vaccinia) Vaccine Adverse Reactions: Vaccinia Immune Globulin and Cidofovir. Last updated September 28, 2009. Available at: <http://www.bt.cdc.gov/agent/smallpox/vaccination/mgmt-adv-reactions.asp>]. The CDC has informed the NCI/CTEP that cidofovir will not be supplied through Strategic National Pharmaceutical Stockpile to investigators involved in CTEP-sponsored protocols utilizing recombinant vaccinia-based vaccines. Thus, investigators should obtain cidofovir for second-line therapy through commercial sources if necessary. Investigators should consult the CDC Clinician Information Line at [name] or the Director's Emergency Operations Center (DEOC) at [contact] regarding appropriateness of therapy and guidance.

5.6 DURATION OF THERAPY

In the absence of treatment delays due to adverse event(s), therapy will continue as per the aforementioned schema. Off therapy criteria is listed in Section 0.

5.7 DURATION OF FOLLOW UP

Subjects will be followed for 1 year after the initial 20 week study course is completed with surveillance cystoscopy or until death, whichever occurs first.

5.8 CRITERIA FOR REMOVAL FROM PROTOCOL THERAPY AND OFF STUDY CRITERIA

Prior to removal from study, effort must be made to have all subjects complete a safety visit approximately 30 days following the last dose of study therapy.

5.8.1 Criteria for removal from protocol therapy

- Intercurrent illness or medical circumstances: if at any time the constraints of this protocol are detrimental to the subject's health, the subject may be removed from protocol therapy. In this event, the reasons for withdrawal will be documented.
- General or specific changes in the subject's condition render the subject unacceptable for further treatment in the judgment of the investigator (investigator discretion).
- Participant requests to be withdrawn from active therapy
- Enroll on another protocol or receives standard of care.
- Unacceptable treatment-related toxicity (DLT) as defined in Section [5.4](#).
- Grade 4 toxicity after vaccinia injection per table below³⁵:

Vaccinia-Related Toxicity Grading	
Grade 1	
	Cutaneous reaction extending to not more than 10 cm from vaccination site
Grade 2	
	Cutaneous reaction extending to more than 10 cm from the vaccination site or any autoinoculation that resolves without sequelae
Grade 3	
	Not applicable
Grade 4	
	Autoinoculation syndrome with sequelae: postvaccinia encephalitis, vaccinia gangrenosum, eczema gangrenosum, or Steven-Johnson syndrome

5.8.2 Off-Study Criteria

- Completed study follow-up period (1 year post treatment)
- Disease progression to muscle-invasive urothelial carcinoma of the bladder
- Subject's request to be taken off study. In this event, the reasons for withdrawal will be documented.
- If subjects are non-compliant with the protocol guidelines, they may be removed from the study at the discretion of the principal investigator.
- Death

5.8.3 Off Protocol Therapy and Off-Study Procedure

Authorized staff must notify Central Registration Office (CRO) when a subject is taken off protocol therapy and when a subject is taken off study. A Participant Status Updates Form from the web site ([https://nih.sharepoint.com/sites/NCI-CCR-OCD-Communications/SitePages/OEC-Administrative---Clinical-Research-\(ADCR\).aspx?Mode=Edit](https://nih.sharepoint.com/sites/NCI-CCR-OCD-Communications/SitePages/OEC-Administrative---Clinical-Research-(ADCR).aspx?Mode=Edit)) main page must be completed and sent via encrypted email to: NCI Central Registration Office [contact].

For participating sites, the Participant Status Updates Form will be supplied by the CCR study coordinator. Send the completed form to the CCR study coordinator.

6 DOSING DELAYS/DOSE MODIFICATIONS

6.1 TICE BCG

The need for BCG dose modification may arise and has been described previously. To review, subjects will receive weekly (+/- 2 days) intravesical doses of BCG (TICE strain, 50 mg) as per usual standard of care for a total of 6 weeks. Urine will be tested weekly prior to each BCG administration and the presence of gross hematuria or a urinary tract infection by urinalysis will result in holding that week's BCG dose and postponing therapy until the following week. Also, at the beginning of each administration, subjects will be queried about urinary symptoms. Complaints of persistent dysuria, urgency, bladder spasms, and/or frequency from previous week's administration that is consistent with Grade 3 or greater toxicity will result in holding BCG administration for that week, supportive care (e.g. medications and hydration), and/or BCG dose reduction the following week at 1/3 normal dose as this can result in less toxicity with similar results for recurrence and progression.³¹ Complaints of non-infective cystitis or hematuria consistent with Grade 2 or higher will result in holding BCG administration for that week. Therapy will resume the following week at if these symptoms are at less than or equal to Grade 1. Subjects will be maintained at this reduced dose if they continue to fail to tolerate full dose therapy.

Future inability to tolerate this reduced dose will result in holding BCG for that week and postponing the BCG until the following week and dropping to 1/6 of the normal dose (details in Section 5.2). Of note, weekly BCG postponement or dose reductions will not alter the vaccination schedule. For example, if the week 5 dose of BCG is withheld, the subject will still receive the next dose of PANVAC™-F on week 7, but the last dose of BCG would be given on week 9 instead of week 8 (assuming that no other BCG postponement is necessary).

6.2 PANVAC™-V (VACCINIA) AND PANVAC™-F (FOWLPOX)

6.2.1 Dosing delay

- Subjects must have recovered to \leq grade 1 toxicity related to vaccine for constitutional symptoms (that are not related to the BCG or medications related to BCG treatments) in order to receive a subsequent vaccination. These constitutional symptoms are listed in Section 8.1.1.1.

- Subjects with \leq grade 2 toxicity not related to vaccine treatment (i.e. attributed to BCG) will remain eligible to receive vaccine.
- Subjects that recover from grade 3 toxicity unrelated to vaccine treatment (i.e. related to BCG) will remain eligible for the vaccine. However, subjects that experience a grade 4 toxicity unrelated to vaccine treatment (i.e. attributed to BCG) will not remain eligible for further vaccine administration.
- If BCG is permanently discontinued, the patient will remain eligible for further vaccine administration in the absence of a grade 4 toxicity.
- Vaccination will be held for $>$ grade 2 proteinuria measured initially by a urine dipstick but confirmed by a 24 hour urine collection.
- If \geq grade 2 nonautoimmune toxicity attributable to the vaccine persists for $>$ 42 days, the subject will not receive further vaccine inoculations and will be removed from the protocol treatment and followed for resolution of toxicity and immune endpoints.
- Subjects who develop grade 3 injection site reactions will have their vaccine held until injection site reaction resolves to grade 2 or less.
- Subjects who develop \geq a grade 2 allergic or autoimmune disease that threatens vital organ function or any \geq grade 3 autoimmunity, not related to a therapeutic response, will be removed from the protocol treatment and followed for resolution of toxicity and immune endpoints. Follow-up will be performed during each vaccination and blood draw interval for immunologic testing as described in Section 11
- Subjects who develop any grade 4 toxicity attributable to the study drug(s) will be removed from the protocol treatment and followed for resolution of toxicity and immune endpoints.
- If a scheduled vaccine dose is missed due to scheduling or logistical issues, the vaccine may be given within 7 days of the appointed time (which resets the appointed date for further vaccinations) or be considered a missed dose. If the subject has a delay in vaccination not due to toxicity during the core phase, the vaccine may be delayed for up to 42 days without removal of the subject from study. BCG administration will not be affected by missed/delayed vaccine administrations.

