5.4 DOSE LIMITING TOXICITY

TICE BCG will be given in the standard dose and schedule as described above. All toxicities observed will be tabulated by maximum grade per subject. A dose limiting toxicity (DLT) will be any grade 3 or greater adverse effect (AE) by CTCAE v5.0 related to the investigational agent and persisting for more than one week and not improving by routine standard of care. In

addition, any grade 3 or greater AE as per a previously published vaccinia toxicity grading scale³³ related to the investigational agent will also be considered a DLT.

Intravesical BCG therapy can lead to common side effects that are usually self-limited, particularly with dose reduction. These side effects include, but are not limited to, gross hematuria, dysuria, frequency, urgency, bladder spasms, and generalized cystitis. These side effects will not be considered a DLT if it is related to BCG and resolves with BCG dose reduction and/or postponing therapy by 1-2 weeks and treating symptoms with conservative management. In contrast, persistent side effects despite dose reduction/postponing of BCG therapy or the development of systemic BCG infection (aka “BCG-osis”) will be considered a DLT.

Severe adverse events due to local instillation of BCG are uncommon. In a retrospective analysis of 2602 patients reported in 1989, the overall rate of serious complications was less than five percent.³⁴ The most common complication was fever >103°F in 2.9 percent followed in decreasing frequency by:

- Significant hematuria (1 percent)
- Granulomatous prostatitis (0.9 percent)
- Pneumonitis and/or hepatitis (0.7 percent)
- Arthralgia (0.5 percent)
- Epididymitis (0.4 percent)
- Sepsis (0.4 percent)
- Rash (0.3 percent)
- Ureteral obstruction (0.3 percent)
- Contracted bladder (0.2 percent)
- Renal abscess (0.1 percent)
- Cytopenia (0.1 percent)

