5.5 GENERAL CONCOMITANT MEDICATION AND SUPPORTIVE CARE GUIDELINES

For the vaccine administration, anti-emetics and anti-diarrheal agents may be administered as required, but are not anticipated to be needed and should not be used prophylactically on the first cycle. The selection of the specific antiemetic regimen is at the discretion of the treating physician. Antiemetic regimens should not include dexamethasone or other steroids.

Other supportive care with blood components, antibiotics, analgesics, general medical therapy, etc., will be delivered as required. Any subjects taking antibiotics for any reason must complete that course of therapy and be free of evidence of further infection before receiving any dose of vaccine. To avoid blunting of the immune response, we will avoid administering corticosteroids or other immunosuppressive agents unless medically indicated.

Symptomatic anemia should be treated with appropriate red blood cell or erythropoietin support.

Thrombocytopenia should be treated conservatively. In the absence of bleeding or a planned invasive procedure, platelet transfusions should be given for a platelet count below 10,000/mm³. If invasive procedures are planned or the subject develops bleeding, platelet transfusions should be administered in accordance with the standard of practice, usually maintaining a platelet count of >50,000/mm³.

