15.4 EVALUATION OF BENEFITS AND RISKS/DISCOMFORTS

BCG is a standard of care treatment and will be used in this study. The biggest risk of using this agent after failing an initial induction course of BCG is progression of disease to muscle-invasive disease. However, this occurs after multiple, failed BCG induction treatments and occurs more often after 2 years of such therapy⁴⁰. In addition, patients will be accurately staged for disease with imaging, TURBT, and in some cases, repeat TURBT. They will be followed quite rigorously throughout the study and thereafter with a planned biopsy between weeks 17-20 to ensure that no progression of disease has occurred during the treatment period. Patients who progress will promptly undergo radical cystectomy. Radical cystectomy and pelvic lymphadenectomy is also considered a standard of care treatment for high grade BCG refractory NMIBC. However, since enrollment into this study requires patients to refuse radical surgery or not be medically fit for surgery, we believe the risk of proceeding with another induction course of BCG is outweighed by its benefit.

Other risks of the use of BCG include local bladder symptoms such as blood in the urine, urinary frequency, urgency of urination, dysuria (pain), and bladder spasms which are often self-limiting and usually resolve within a week by withholding BCG and administering standard of care medications (e.g. anti-inflammatories, anti-spasmodics, hydration, etc.). Finally, a rare potential risk of BCG administration is development of “BCG-osis” which is a form of bacteremia/urosepsis or systemic BCG infection that occurs with BCG administration on very rare occasions. In this event, patients will be taken off the study and treated with anti-microbials as per recommendations by infectious disease consultants. The addition of PANVACTTM is unknown but given the relative safety of both agents and different routes of administration, we presume that the risk is minimal.

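### Section 15.4 takes systemic BCG infection off study against 5.7, and 5.8.1 and 6.2.1 disagree on PANVAC after a recovered grade 3 BCG DLT

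*Combined protocol and SAP*

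**What the plan says.** **Follow-up.** In its account of BCG risks, Section 15.4 says of systemic BCG infection: "In this event, patients will be taken off the study and treated with anti-microbials". Section 5.7 says "Subjects will be followed for 1 year after the initial 20 week study course is completed", with death as the only earlier end. The off-study list in Section 5.8.2 has five items: completed follow-up, muscle-invasive progression, the subject's request, non-compliance and death. Section 5.8.3 has the registration office notified of two separate events, coming off protocol therapy and coming off study.

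**Dosing.** Section 5.4 exempts BCG side effects that resolve with dose reduction or a postponement of one to two weeks plus symptomatic care. It then counts as DLTs "persistent side effects despite dose reduction/postponing of BCG therapy or the development of systemic BCG infection". Section 5.8.1 lists, as a criterion for removal from protocol therapy, "Unacceptable treatment-related toxicity (DLT) as defined in Section" 5.4, and does not distinguish BCG from PANVAC. Two bullets in Section 6.2.1 point the other way: "Subjects that recover from grade 3 toxicity unrelated to vaccine treatment (i.e. related to BCG) will remain eligible for the vaccine", and "If BCG is permanently discontinued, the patient will remain eligible for further vaccine administration in the absence of a grade 4 toxicity". Section 5.5 adds that a subject on antibiotics "must complete that course of therapy and be free of evidence of further infection before receiving any dose of vaccine".

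**The concern.** On follow-up, the 15.4 instruction applies to both arms and is triggered by a treatment complication, not by disease. A patient who leaves under it stops contributing to the primary endpoint before anyone has looked for recurrence. Censoring of that kind is hard to defend as unrelated to outcome, and it is avoidable, because the infection is a reason to stop treatment but not to stop cystoscopy.

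On dosing, a site holding a combination-arm patient with a declared DLT that has since recovered finds two instructions. One section ends all protocol therapy; another keeps the vaccine going. No cross-reference says which prevails, so two sites could treat the same patient differently.

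**Working it through.** No stated figure is in dispute. The check sets the rules side by side and then sizes them.

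**1. Timing of the off-study rule.** BCG is given in weeks 3 to 8 when there are no delays (5.1.1). The first planned cystoscopy and biopsy are at weeks 17 to 20 (5.1.5). Recurrence-free survival is counted from week 3 (12.1.1.3).

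- Time on the endpoint clock for a patient who leaves between weeks 3 and 8: 3 − 3 = 0 to 8 − 3 = 5 weeks.
- Time still to run to the earliest assessment: 17 − 8 = 9 to 17 − 3 = 14 weeks.

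Such a patient has no post-baseline disease assessment.

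**2. Dosing rules by situation (combination arm, BCG toxicity).**

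| Situation | 5.4 with 5.8.1 | 6.2.1 | Conflict |
|---|---|---|---|
| Grade 3, resolved with reduction or a 1–2 week postponement | Not a DLT | Eligible | No |
| Grade 3, persisted, not recovered | Remove | Recovery bullet withholds vaccine | None in practice |
| Grade 3, persisted, recovered after BCG stopped | Remove | Eligible under both bullets | **Yes** |
| Grade 2, persisted | Unclear: the BCG sentence gives no grade, the general DLT definition starts at grade 3 | Eligible | Arguable |
| Grade 4 | Remove | Not eligible | No |
| Systemic infection below grade 4, cleared | Remove; 15.4 also takes the patient off study | Eligible on its own wording | Not open: 5.8.1 and 15.4 both stop vaccine |

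For the third row, suppose the reduction steps in 5.2.3.3 are followed in full after k full doses: hold, one third, hold, one sixth, stop. The stop week is 3 + (k − 1) + 5, that is week 8, 9 or 10 for k = 1, 2 or 3. With k = 4 all six doses are given, so BCG is not stopped early. The boosts still due are those at weeks 11 and 15, so at most 2 of the 4 fowlpox boosts are at stake per affected patient.

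**3. Number of patients off study.** Inputs: accrual ceiling N = 54 (14.1). From 5.4: sepsis 0.4%, pneumonitis and/or hepatitis 0.7%, and a separate sepsis estimate of 1 in 15,000. Formulas: expected number = N × r; chance of at least one = 1 − (1 − r)^N.

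- r = 1/15,000: 54/15,000 = 0.0036 patients.
- r = 0.004: 54 × 0.004 = 0.216 patients; 1 − 0.996^54 = 0.195.
- r = 0.004 + 0.007 = 0.011, assuming no overlap and that all of these count as systemic infection: 54 × 0.011 = 0.594 patients; 1 − 0.989^54 = 0.45.

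With the planned 49 patients, the 0.4% line becomes 0.196 patients and a chance of 0.178. Each patient lost costs at most 1 of the 40 events expected at N = 49, or 2.5%.

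**The case against.** **Section 6.2.1 can be read as the governing rule.** Section 5.3 sends the reader to Section 6 for dose modifications, 6.2.1 addresses permanent BCG discontinuation by name, and 5.8.1 is a general list. Sections 5.2.3.4 and 6.1 also keep PANVAC on schedule when BCG is delayed or reduced. This shows the likely intent, which is to handle the two agents separately, and it decides where the correction belongs. It does not remove the contradiction. Those passages concern delay and reduction, not a DLT. Section 5.8.1 adopts a DLT definition that expressly covers BCG effects, and 6.2.1 does not present itself as an exception to it.

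**Section 15.4 is narrative, and 5.8.2 is not exhaustive.** Both points stand. Sections 5.1.6 and 5.2.2.3 take patients off study at confirmed recurrence, which 5.8.2 also omits, so absence from that list is weak evidence by itself. But recurrence is the endpoint, and leaving then loses nothing for the primary analysis. The case rests mainly on 5.7 and on the separation of statuses in 5.8.3. Several bullets in 6.2.1 also end treatment for toxicity while keeping the patient under follow-up. If 15.4 only meant off treatment, that is a reason to correct the phrase.

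**Readings that go too far.** A reader might infer that cleared systemic BCG infection is a further open dosing conflict, since 5.5 only delays vaccine and 6.2.1 allows it short of grade 4. The documents do not support this: 5.8.1 and 15.4 both stop vaccine after that event. A reader might also see a breach of 14.4.2, which wants every included patient assessed for response. That section governs who is analysed despite deviations; it does not set the length of follow-up, and a patient who leaves early can be included and censored.

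**Conclusion.** Both contradictions hold as written and both are minor.

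The off-study wording is the one with a statistical consequence: follow-up for the primary endpoint ends early for a treatment-related reason. It would probably touch no patient or one, about 0.2 of 54 at 0.4%. That figure assumes the quoted sepsis rate is a fair proxy for systemic BCG infection; across the rates in 5.4 the range is 0.0036 to 0.6.

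The dosing contradiction is clear only for grade 3 BCG toxicity that persisted despite reduction or postponement and then recovered once BCG was stopped. Its frequency cannot be computed. A reader might take the statement that "the overall rate of serious complications was less than five percent" as the rate. It covers all serious BCG complications, and nothing says how many were DLTs below grade 4, led to permanent discontinuation and later recovered.

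Alpha, power and sample size do not change. Sections 8 and 8.3 record closure with CTEP on 5/1/2019, so dosing is probably over. The remaining value then lies mainly in how affected patients are listed and analysed.

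**What to change.** 1. **Section 15.4.** Replace the off-study wording with removal from protocol therapy, and state that surveillance cystoscopy continues to one year under 5.7. If follow-up has already stopped for such a patient in either arm, retrieve outside cystoscopy and pathology records where consent allows, and keep the patient in the primary analysis. Footnote 10 to the study calendars already uses outside records for patients who cannot return after week 20.

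2. **Section 5.8.1, DLT bullet.** Add: *except that a DLT below grade 4 attributed to BCG alone, other than systemic BCG infection, stops BCG only; PANVAC continues under 6.2.1 after recovery.* This follows the apparent intent of Section 6. If the sponsor wants PANVAC stopped instead, both the recovery bullet and the BCG-discontinuation bullet in 6.2.1 must be amended; changing one would leave the contradiction in place.

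3. **Section 6.2.1.** Name systemic BCG infection as an exception to continued vaccine eligibility.

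4. **If dosing is complete.** List each combination-arm patient whose BCG was permanently stopped, with the reason, DLT status and any later boosts.

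The cost is a few lines of text, one short listing and, at most, records for one or two patients. No visits or patients are added.
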